### 3. Introduction

Overactive bladder is a stressful and disruptive chronic disorder that affects more than 16% of the adult population [1], an estimated 42 million adults in the just the United States alone. The symptoms of OAB cause millions of individuals to suffer with a decrease in their quality of life and put them at increased risk of falls, bone fractures due to falls and higher rates of anxiety and depression

OAB is characterized by four symptoms; urgency, frequency, nocturia, and urge incontinence[2]. Urgency is the complaint of a sudden, irresistible desire to pass urine which often is difficult to resist. Frequency is the number of voids per day. In OAB, there are usually 8 or more voiding episodes during waking hours. Nocturia is the number of voids per night. In OAB, the complaint of sleep interruption due to the need to void is 1+ times, per night. Urge incontinence is the involuntary leakage of urine, associated with sudden compelling desire to void. In order to be diagnosed, these symptoms or a combination of them, must be present without a pathologic or metabolic component causing them[3].

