### **7.5. Visit 1 - Screening 2 (EMG evaluation)**

This procedure will evaluate if EMG signals can be recorded during stimulation of the tibial nerve with the wearable bladder modulation system.

Step	Action
1.	Screening evaluations will be collected including (using a 3-day Bladder Diary): 

1. Number of daytime voids

2. Number of urge events

3. Number of nighttime voids

4. Number of urge incontinence events

Note	Only subjects that meet the inclusion/exclusion criteria with regard to the Bladder Diary will proceed to EMG testing.
2.	Only delegated, qualified, site personnel will instruct the subject on how to place the Test Article on the foot and ankle area.
3.	Once the Test Article is placed, site personnel will use the Test Article to stimulate the tibial nerve, evaluate EMG signals and instruct the subject how to use the Test Article.
4.	The subject will be asked to rate various sensations experienced during the stimulation therapy.
5.	Subject will be enrolled in the study and given a subject ID.
Note	Only subjects that have a detectable EMG and find the stimulation sensation tolerable will be eligible for enrollment.

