### **13.2. Analysis of Efficacy and Sample Size**

Using data collected at each of Study Visits 2, 3, and 4, percent change from screening at each time point will be calculated for each patient with respect to frequency of OAB symptoms, including 3-day daily averages of daytime voids, urge events, nighttime voids, and urge incontinent events. The maximum percent improvement across the four symptoms will also be calculated at each time point as a composite endpoint. Percent improvement in daily average total voids relative to an upper normal limit of 8, will also be calculated, and will be bounded below at 0% for patients not achieving improvement and bounded above at 100% for patients achieving or surpassing the upper normal limit of 8. Longitudinal analyses will be performed using repeated measures models to assess and describe trends over time with respect to these endpoints. At individual time points, the one-sample T-test will be performed at significance level  $\alpha=0.05$  within each treatment group and for the pooled study groups to assess the mean percent improvements, with 95% confidence intervals for mean percent improvements also calculated. The percent change endpoints are not likely to have approximately normal distributions, but the sample size is considered sufficient such that mean values will be approximately normally distributed, justifying the use of the T-tests. If there is concern with the distributions, then the Wilcoxon signed rank test will be used as an alternative to the one-sample T-test.

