# 3-Day Bladder Diary Visit #

Subject ID: \_\_\_\_\_

Subject Initials: \_\_\_\_\_

1. Choose **3 days** (entire 24 hours) to complete this record - they **do not** have to be in a row. Pick days during which it will be convenient to measure **every** void.
2. Begin recording when you wake up in the morning and continue for a full **24 hours**.
3. Make a separate entry each time you **void, leak** or have anything to **drink**.
4. Record each time you notice a leak - please indicate how much using a scale from 1-3 (1=drops/damp, 2=wet/soaked, 3=bladder emptied/voided). Record if you felt an "urge" with the leak (yes or no).

Time of Day	Fluid Intake (oz)	Leak Amount (1-3)	Activity with Leak	Urge with Leak (yes or no)	Comments
7:15 am					
7:45 am	2 oz				
9:00 am		2		Yes	
10:30 am	3 oz	1	Sneezing	No	

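### The bladder diary asks about urge only when there is a leak, so urge events cannot be counted apart from urge incontinence, and no rule separates day voids from night voids

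*Combined protocol and SAP*

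**What the plan says.** Section 13.2 calculates percent change from screening for "3-day daily averages of daytime voids, urge events, nighttime voids, and urge incontinent events". It takes the largest improvement across the four as a composite at each time point. It counts a subject as a composite responder if any one symptom improves by 50%. Section 7.5 takes the same counts from the screening diary and lists "Number of urge events" as an item separate from urge incontinence.

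Section 3 defines urgency without reference to leakage: "Urgency is the complaint of a sudden, irresistible desire to pass urine which often is difficult to resist". It describes nocturia as voids per night that interrupt sleep.

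The diary's instruction 3 says when to write something down: "Make a separate entry each time you void, leak or have anything to drink". Instruction 4 is the only one that mentions urge: "Record if you felt an 'urge' with the leak (yes or no". The matching column is headed "Urge with Leak (yes or no". Instruction 2 sets the recording period: "Begin recording when you wake up in the morning and continue for a full 24 hours". No instruction asks for the time of going to bed or getting up.

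Section 6.1 states that there is no blinding. Section 9 says that the investigator collects all outcome variables. No section says how urge events are derived from the diary, where night begins and ends, or who assigns a void to day or night.

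**The concern.** Urgency is the first of the four symptoms that section 3 lists, and it has its own endpoint and responder rate. If the form does not ask for it, that endpoint repeats urge incontinence under another name, and urgency that was never written down cannot be recovered at analysis. If sites improvise instead, up to 12 of them may count differently. The composite and its responder rate inherit the fault.

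The day/night split is a second, smaller gap. Two of the four counts depend on a boundary that is neither recorded nor defined, in a trial where everyone knows the arm.

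**Working it through.** **1. The plan's own figures, and whether they depend on this point.**
- Enrolment: 80 / (1 − 0.15) = 94.1, against about 94 stated.
- Power: section 13.2 assumes a median improvement of 15% and that 25% of patients reach 50%. The log ratio then has mean ln 0.85 = −0.163 and SD (ln 0.85 − ln 0.5) / 0.6745 = 0.531 / 0.6745 = 0.787. Improvement toward 8 voids per day is (B − F) / (B − 8), limited to 0–100%, where B is baseline and F is follow-up. Success means that the lower 95% confidence limit reaches the threshold. The plan gives no value for B, so B is an assumption here. The results come from 20,000 simulated trials.

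| Assumed baseline voids/day | n = 80, mean at least 25% (plan: 95.6%) | n = 40, mean at least 20% (plan: 90.8%) |
|---|---|---|
| 14 | 98.6% | 95.2% |
| 16 | 96.2% | 91.8% |
| 20 | 87.8% | 84.4% |

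The stated powers are matched to about one point at a baseline near 16. The calculation uses total voids only. It needs neither an urge field nor a day/night split, so nothing below changes it.

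**2. What the diary prompts, set against what the endpoints need.**

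| Event | Entry prompted? | Urge asked? |
|---|---|---|
| Urge ending in a leak | Yes | Yes |
| Urge ending in a dry void | Yes, as a void | Not by any instruction |
| Urge resisted, no void or leak | No | No |

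The only prompted urge count is therefore leaks with urge = yes, which is also the urge incontinence count. The two endpoints coincide by construction.

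**3. Subjects without leaks.** Entry requires an average of 10 or more frequency events per day, not leakage. Section 7.6 limits the IIQ-7 to those with incontinence, so dry subjects are expected. Their baseline urge count on this form is 0, and percent change (F − 0) / 0 is undefined. Their urge incontinence change is undefined on any form. What the diary adds is that urge events are lost as well.

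**4. Effect on the composite (illustration).** Assume that each symptom has a 25% response rate with equal correlation between symptoms. At zero correlation, four components give 1 − 0.75⁴ = 68% and three give 1 − 0.75³ = 58%. By simulation, the fall is from 52% to 46% at correlation 0.5 and from 36% to 34% at 0.9.

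**5. Day/night split (illustration).** The plan gives no baseline number of night voids. Relabelling one void per night across three diary days changes the night count as follows:
- 1 per night: 3/3 = 100%
- 2 per night: 3/6 = 50%, the responder threshold
- 3 per night: 3/9 = 33%, below the threshold

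Relabelling a single void over the whole diary at 2 per night changes the count by 1/6 = 17%.

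**The case against.** **The form may hold more than the text shows.** The table was read by machine. No void column appears, although instruction 1 tells subjects to measure voids, the sample 7:15 am row is blank, and the polyuria exclusion needs daily urine output. The instructions are not a full list of fields either: the activity and comments columns and the pad count are not mentioned in them. A lost column for urge with a void therefore cannot be ruled out, which is why confidence is medium. A reader might infer that the form has no way to mark a void. The documents do not support that. What survives is that the intact instructions tie urge only to a leak, and that resisted urgency prompts no entry whatever columns exist. Comments are unprompted, and the OAB-q rates bother over four weeks, so neither supplies event counts.

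**Unblinded staff may not be splitting the voids.** A reader might infer that site staff who know the arm decide what is day and what is night. No section says so. Each entry carries a clock time and recording starts on waking, so one fixed clock rule could be applied alike in both arms. The supportable statement is that no rule is prespecified, which leaves room for judgement. The relabelling figures in the illustration show sensitivity, not bias between arms. They need relabelling at follow-up but not at screening, and the screening diary precedes randomization.

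**The harm is limited.** A duplicated component makes composite response less likely, so it does not inflate apparent benefit. The endpoint used for sample size is untouched. Both points stand and set the severity.

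**Conclusion.** The concern holds in this form: by the diary's written instructions, urge events cannot be obtained separately from urge incontinence events, and section 13.2 gives no derivation rule for urge events or night voids. One of the four symptom endpoints is a duplicate for subjects who leak and is not calculable for subjects who do not. The composite and its responder rate rest on at most three distinct measures. Two further counts lack a day/night boundary.

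The size of the effect on the composite depends on an assumed 25% response per symptom: a loss of about 2 to 10 percentage points over correlations from 0.9 to 0. The effect on night voids depends on an assumed baseline count.

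A reader might infer that the trial's sizing or its total-voids result is compromised. It is not: that endpoint and every stated power figure are unaffected. This is a should-fix point, with medium confidence because of the possible lost column.

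**What to change.** 1. **Diary.** Ask urge yes/no for every void, ask for an entry for any urge without a void or leak, and record bedtime and rising time for each 24 hours.
2. **Section 13.2.** Define urge events as all entries with urge = yes, and night voids as voids between the two recorded times. Derive both by program, identically in both arms.
3. **Subjects whose baseline diary was on the old form.** Do not compare an old-form baseline with a new-form follow-up. Drop urge events as a separate endpoint and as a composite component for them, and apply one prespecified clock window for night at all their visits.

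**Cost.** Subjects record slightly more. The diary is part of the protocol's Appendix A, so the change is an amendment that needs approval by the sponsor, the investigator and the IRB/IEC under section 15 before use; notification is not enough. Subjects already enrolled will have no separate urge-event result. No visit or procedure is added.

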## 3-Day Bladder Diary Visit #

**Subject ID:** \_\_\_\_\_

**Subject Initials:**

## Number of Pads for full 24 hours:

**SIGNATURE**

I have reviewed the recorded information for this visit and verified that it is complete and accurate.

**Authorized Signature**

Date

# OAB-q (HQL) Form- Visit

Subject ID: \_\_\_\_\_

Subject Initials: \_\_\_\_\_

This questionnaire asks about how much you have been bothered by selected bladder symptoms during the past 4 weeks. Please mark the box that best describes the extent to which you were bothered by each symptom during the past 4 weeks. There are no right or wrong answers. Please be sure to answer every question.

During the past 4 weeks, how bothered were you by...	(1)	(2)	(3)	(4)	(5)	(6)
1. Frequent urination during day-time hours	Not at all	A little bit	Somewhat	Quite a bit	A great deal	A very great deal
2. An uncomfortable urge to urinate	Not at all	A little bit	Somewhat	Quite a bit	A great deal	A very great deal
3. A sudden urge to urinate with little or no warning	Not at all	A little bit	Somewhat	Quite a bit	A great deal	A very great deal
4. Accidental loss of small amounts of urine	Not at all	A little bit	Somewhat	Quite a bit	A great deal	A very great deal
5. Nighttime urination	Not at all	A little bit	Somewhat	Quite a bit	A great deal	A very great deal
6. Waking up at night because you had to urinate	Not at all	A little bit	Somewhat	Quite a bit	A great deal	A very great deal
7. An uncontrollable urge to urinate	Not at all	A little bit	Somewhat	Quite a bit	A great deal	A very great deal
8. Urine loss associated with a strong desire to urinate	Not at all	A little bit	Somewhat	Quite a bit	A great deal	A very great deal

This questionnaire asks about how much you have been bothered by selected bladder symptoms during the past 4 weeks. Please circle what best describes the extent to which you were bothered by each symptom during the past 4 weeks. There are no right or wrong answers. Please be sure to answer every question.

During the past 4 weeks, how often have your bladder symptoms...	(1)	(2)	(3)	(4)	(5)	(6)
9. Made you carefully plan your commute?	None of the time	A little of the time	Some of the time	A good bit of the time	Most of the time	All of the time
10. Caused you to feel drowsy or sleepy during the day?	None of the time	A little of the time	Some of the time	A good bit of the time	Most of the time	All of the time
11. Caused you to plan 'escape routes' to restrooms in public places?	None of the time	A little of the time	Some of the time	A good bit of the time	Most of the time	All of the time

# OAB-q (HQL) Form- Visit

Subject ID: \_\_\_\_\_

Subject Initials: \_\_\_\_\_

12. Caused you distress?	None of the time	A little of the time	Some of the time	A good bit of the time	Most of the time	All of the time
13. Frustrated you?	None of the time	A little of the time	Some of the time	A good bit of the time	Most of the time	All of the time
14. Made you feel like there is something wrong with you?	None of the time	A little of the time	Some of the time	A good bit of the time	Most of the time	All of the time
15. Interfered with your ability to get a good night's rest?	None of the time	A little of the time	Some of the time	A good bit of the time	Most of the time	All of the time
16. Caused you to decrease your physical activities (exercising, sports, etc.)?	None of the time	A little of the time	Some of the time	A good bit of the time	Most of the time	All of the time
17. Prevented you from feeling rested upon walking in the morning?	None of the time	A little of the time	Some of the time	A good bit of the time	Most of the time	All of the time
18. Frustrated your family or friends?	None of the time	A little of the time	Some of the time	A good bit of the time	Most of the time	All of the time
19. Caused you anxiety or worry?	None of the time	A little of the time	Some of the time	A good bit of the time	Most of the time	All of the time
20. Caused you to stay home more often than you would prefer?	None of the time	A little of the time	Some of the time	A good bit of the time	Most of the time	All of the time
21. Caused you to adjust your travel plans so that you are always near a restroom?	None of the time	A little of the time	Some of the time	A good bit of the time	Most of the time	All of the time
22. Made you avoid activities away from restrooms (i.e., walks, running, hiking)?	None of the time	A little of the time	Some of the time	A good bit of the time	Most of the time	All of the time
23. Made you frustrated or annoyed about the amount of time you spend in the restroom?	None of the time	A little of the time	Some of the time	A good bit of the time	Most of the time	All of the time
24. Awakened you during sleep?	None of the time	A little of the time	Some of the time	A good bit of the time	Most of the time	All of the time
25. Made you worry about odor or hygiene?	None of the time	A little of the time	Some of the time	A good bit of the time	Most of the time	All of the time

# IIQ-7 SF Form- Visit

Subject ID: \_\_\_\_\_

Subject Initials: \_\_\_\_\_

Some people find that accidental urine loss may affect their activities, relationships, and feelings. The questions below refer to areas in your life that may have been influenced or changed by your problem. For each question, circle the response that best describes how much your activities, relationships, and feelings are being affected by urine leakage.

Has urine leakage affected your:	Not at all	Slightly	Moderately	Greatly	Subject Score
1. Ability to do household chores (cooking, housecleaning, laundry)?	0	1	2	3	—
2. Physical recreation such as walking, swimming, or other exercise?	0	1	2	3	—
3. Entertainment activities (movies, concerts, etc.)?	0	1	2	3	—
4. Ability to travel by car or bus more than 30 minutes from home?	0	1	2	3	—
5. Participation in social activities outside your home?	0	1	2	3	—
6. Emotional health (nervousness, depression, etc.)?	0	1	2	3	—
7. Feeling frustrated?	0	1	2	3	—
TOTAL					—

**Reference.** Uebersax, J.S., Wyman, J. F., Shumaker, S. A., McClish, D. K., Fantl, J. A., & the Continence Program for Women Research Group. (1995). Short forms to assess life quality and symptom distress for urinary incontinence in women: The incontinence impact questionnaire and the urogenital distress inventory. *Neurology and Urodynamics*, 14, 131-139.

SIGNATURE	
I have reviewed the recorded information for this visit and verified that it is complete and accurate.	
_____	 D  D  M  M  M  Y  Y  Y  Y
Authorized Signature	Date

# PGIC – Visit #

Subject ID: \_\_\_\_\_

Subject Initials: \_\_\_\_\_

Chief Complaint: _____		
Since beginning treatment how would you describe the change (if any) in ACTIVITY LIMITATIONS SYMPTOMS, EMOTIONS and OVERALL QUALITY OF LIFE, related to your condition? (tick ONE box)		
1. No change (or condition has got worse)		
2. Almost the same, hardly any change at all		
3. A little better, but no noticeable change		
4. Somewhat better but the change has not made any real difference		
5. Moderately better, and a slight but noticeable change		
6. Better, and a definite improvement that has made a real and worthwhile difference		
7. A great deal better and a considerable improvement that has made all the difference		
In a similar way, please circle the number below, that matches your degree of change since beginning care at this clinic:		
<hr/> 0      1      2      3      4      5      6      7      8      9      10 <hr/>		
Much Better	No Change	Much Worse

**Reference:** Hurst H, Bolton J. Assessing the clinical significance of change scores recorded on subjective outcome measures. J Manipulative Physiol Ther 2004;27:26-35.

## SIGNATURE

I have reviewed the recorded information for this visit and verified that it is complete and accurate.

D    D    M    M    M    Y    Y    Y    Y

Authorized Signature

Date

# I-QoL – Visit #

Subject ID: \_\_\_\_\_

Subject Initials: \_\_\_\_\_

ALB Domain					
1. I worry about not being able to get to the toilet on time	Extremely	Quite a bit	Moderately	A little	Not at all
2. I worry about coughing/sneezing because of my incontinence	Extremely	Quite a bit	Moderately	A little	Not at all
3. I have to be careful standing up from sitting	Extremely	Quite a bit	Moderately	A little	Not at all
4. I worry about where toilets are in new places	Extremely	Quite a bit	Moderately	A little	Not at all
5. It's important to me to make frequent trips to the toilet	Extremely	Quite a bit	Moderately	A little	Not at all
6. It's important to plan every detail in advance because of my incontinence	Extremely	Quite a bit	Moderately	A little	Not at all
7. I have difficulty getting a good night's sleep because of my incontinence	Extremely	Quite a bit	Moderately	A little	Not at all
8. I have to watch how much I drink because of my incontinence	Extremely	Quite a bit	Moderately	A little	Not at all
PSI Domain					
9. I feel depressed because of my incontinence	Extremely	Quite a bit	Moderately	A little	Not at all
10. I don't feel free to leave home for long periods of time because of my incontinence	Extremely	Quite a bit	Moderately	A little	Not at all
11. I feel frustrated because my incontinence prevents me doing what I want	Extremely	Quite a bit	Moderately	A little	Not at all
12. My incontinence is always on my mind	Extremely	Quite a bit	Moderately	A little	Not at all
13. My incontinence makes me feel unhealthy	Extremely	Quite a bit	Moderately	A little	Not at all
14. My incontinence makes me feel helpless	Extremely	Quite a bit	Moderately	A little	Not at all
15. I get less enjoyment out of life because of my incontinence	Extremely	Quite a bit	Moderately	A little	Not at all
16. My incontinence limits my choice of clothing	Extremely	Quite a bit	Moderately	A little	Not at all
17. I worry about having sex because of my incontinence	Extremely	Quite a bit	Moderately	A little	Not at all

## I-QoL – Visit #

**Subject ID:** \_\_\_\_\_

**Subject Initials:** \_\_\_\_\_

SE Domain					
18. I worry about others smelling urine on me	Extremely	Quite a bit	Moderately	A little	Not at all
19. I worry about my incontinence getting worse as I get older	Extremely	Quite a bit	Moderately	A little	Not at all
20. I worry about being embarrassed or humiliated by my incontinence	Extremely	Quite a bit	Moderately	A little	Not at all
21. I worry about wetting myself	Extremely	Quite a bit	Moderately	A little	Not at all
22. I feel I have no control over my bladder	Extremely	Quite a bit	Moderately	A little	Not at all

## SIGNATURE

I have reviewed the recorded information for this visit and verified that it is complete and accurate.

A horizontal sequence of 10 boxes. The first two boxes are labeled 'D', the next three are labeled 'M', and the last five are labeled 'Y'.

